# 6.3.10 Medical care upon termination of the clinical investigation

The study participants will not receive any study-specific treatment after their final study visit. Any further treatment, if needed, will be proposed to the subject by the investigator at their discretion.

## 6.3.11 Screening failures, withdrawals, and completer

## Initial treatment phase

- Subjects who have signed the ICF but are not randomized and are not treated for any reason will be considered as screening failures. Data for screening failures will be documented in appropriate forms (e.g., Subject Screening/Enrollment Log). Screening data for these subjects will be kept in the Investigator's File. The type of data to be entered in the eCRF, if any, will be defined in the eCRF Completion Guidelines.
- Subjects who prematurely discontinue the investigation after receiving at least one dose of the device and who are not screening failures will be defined as withdrawals / dropouts.
- Subjects who complete the initial treatment phase (incl. Visit 9 (SV1)) but do not participate in the optional repeat-treatment phase are defined as completer (initial treatment phase).

## Optional repeat-treatment phase including screening phase for repeat-treatment

- Subjects who enter the screening phase for optional repeat-treatment and
  - who are not eligible for the repeat-treatment phase and who are not treated for any reason during repeat-treatment phase will be considered as screening failures for repeat-treatment (SV1, SV2, SV3, SV4, RT1)
  - who are eligible but do not participate in the optional repeat-treatment phase will be considered as completer (initial treatment phase)
- Subjects who prematurely discontinue the investigation after receiving at least one dose of the device at Visit RT1 will be defined as withdrawals / dropouts.

• Subjects who complete the repeat-treatment phase (incl. Visit RT 5) are defined as completer (repeat-treatment phase).

# 6.3.12 Subject identification, privacy and confidentiality

Subjects' privacy and data confidentiality will be protected in line with the principles of Good Clinical Practice (GCP), the European General Data Protection Directive (GDPR), Health Insurance Portability and Accountability Act (HIPAA) and other applicable international and national requirements. Personal subject data transferred to CROMA-PHARMA GmbH in Austria should be in compliance with the European GDPR. Subjects will provide authorization for use of their personal data in accordance with the applicable regulations regarding privacy and data protection.

A unique numerical subject identification code will be assigned to each subject at screening. The format of the codes will be defined in the CRF Completion Guidelines. The investigator will assign the codes in ascending order, in line with the order of the informed consent date and time.

The investigator must ensure that anonymity of the subjects will be maintained and that their identities are protected from unauthorized parties.

In the eCRF or any other document submitted to the sponsor or sponsor's representative, subjects must be identified only by their identification codes; use of names, initials, complete birthdates, addresses, telephone numbers, electronic addresses or similar information is prohibited.

The investigator will keep the Subject Identification Log (including complete name, date of birth, and contact details of each subject). The investigator must maintain these documents in strict confidence.

For GCP compliance, all subjects will be informed and consented regarding the access to their personal investigation-related data by the monitors, auditors and inspectors of the clinical investigation, as well as transmission of their coded data to the sponsor or sponsor's representative and data retention for the duration defined in section 8.4. Professionals with access to subjects' data for monitoring, audits and inspections are bound to preserve strict confidentiality.

This CIP, other investigation-related documentation, collected data and all other information generated will be held in strict confidence. No information concerning the clinical investigation, nor the data collected will be released to any unauthorized third party without prior written approval of the sponsor.

#### Clinical photography

Besides *live* assessments by the blinded evaluator at the site, midface volume deficit will additionally be assessed by a central independent blinded photographic reviewer using photographs (see section 6.4.13). In addition, the photographs will be used for volumetric change measurement (see section 6.4.12) and modified GAIS assessment by the blinded evaluator at the site and subject (see section 6.4.16).

All photographs are submitted to the photo provider in a non-masked manner. During the study, all photographs will be stored in the data base of the photo provider in a non-masked and a masked version, respectively, to allow for review and assessments as required. Image masking will occur during the monitoring process and a 100% quality check will be completed by the photo provider to ensure all images are de-identified before they are forwarded to the sponsor. Details will be given in a separate manual.

Photographs used for publication purposes will *not* reveal the subject's identity. For this purpose, subject's eyes will either not appear on the photographs or will be masked with e.g., a black bar; other attributes visible on the photographs that could identify a subject (e.g., characteristic scars, tattoos).

Subjects will be explicitly informed about these matters when obtaining written informed consent.

## 6.4 Assessments and procedures

Assessments and procedures that will be performed during the investigation are described below. The exact timing of each assessment is indicated in Table 1 to Table 3 and in section 6.5.

It is the treating investigator's obligation to assure documentation of all relevant data in the subject's source record and the eCRF, such as medical history and concomitant diseases, date of enrollment into the clinical investigation, visit dates, results of examinations, application of the device, AEs and device deficiencies.

All subject questionnaires assessing improvement and satisfaction with appearance and outcome (i.e., modified GAIS, FACE-QTM) should preferably be done at the beginning of the respective visit to avoid potential influence of investigator's comments on subject's perception during the visit.

**Important note:** The assessments and procedures described in the following sections must ONLY be conducted by the treating investigator (or trained site staff, if applicable), except for the MVDSS, NLF-SRS and modified GAIS rating, that will be done by the blinded evaluator at the site. The central independent blinded photographic reviewer will conduct MVDSS assessment (see section 6.4.13).

To ensure consistency of effectiveness assessments over the study duration, it is preferred that the same person performs the same assessments on the same subject across all visits.

Treatment-related procedures are described in section 6.2.2, AE and device deficiency collection procedure in section 14.9. All other assessments and procedures are described below.

#### Actions during ongoing COVID-19 pandemic

During COVID-19 pandemic situation, special risk mitigation procedures need to be performed to protect the safety of subjects, site personnel and other persons involved. Possible mitigation measures to be taken into consideration by the study sites are described in section 4.4.

In addition, a separate CIP addendum (see section 4.4) gives detailed information about the possible mitigation measures and alternative procedures in case of restrictions during the pandemic.

If the conduct of visits or assessments of a specific subject is affected by the COVID-19 situation this should be documented in the subject's source records.

#### 6.4.1 Demographic data

Information on subject's year of birth, gender, race and ethnicity will be collected. All demographic data will be documented in the subject's source record and in the eCRF.

#### 6.4.2 *Fitzpatrick skin types*

The Fitzpatrick skin type (FST) scale [44] is a widely used numerical classification scheme for human skin color shown in Table 18.

Skin type	Characteristics	
1	Always burns easily, never tans	
II	Always burns easily, tans minimally	
III	Burns moderately, tans gradually (light brown)	
IV	Burns minimally, always tans well (moderate brown)	
V	Rarely burns, tans very well (moderate brown)	
VI	Never burns, deeply pigmented	

Table 18. Fitzpatrick skin types.

Skin type of the subject will be documented in the subject's source record and in the eCRF.

Note: Enrollment levels for subjects of all FST is encouraged (see section 6.3.2 for details).

#### 6.4.3 Body weight measurement

For body weight measurement, the subject must stand barefoot and wear light indoor clothing. Body weight will be recorded to the nearest kilogram in the subject's source record and the eCRF.

Any findings in the body weight measurement at Screening (Visit 1) will be recorded in the subject's source record and in the eCRF as medical history (see section 6.4.5).

Any changes of clinical relevance (*significant* weight loss or weight gain) compared to the Screening (Visit 1) measurement may represent an AE. The Investigator will evaluate if the change is due to a medical reason (e.g., an accompanying disease like metabolism disorders or cancer, unintended appetite gain/loss, edema), and - if medically reasonable - will record the diagnosis in the subject's source record and document in the eCRF as an AE (see section 14).

## 6.4.4 Pregnancy test

In females of childbearing potential, including women who are postmenopausal for less than twelve months, urine pregnancy tests will be performed using a dipstick test. The result will be recorded in the subject's source record and the eCRF.

In case of positive test result at Screening (Visit 1) the subject must not be enrolled. Any female subject who becomes pregnant while participating in the investigation must be withdrawn from the study (also see section 6.3.6).

The Investigator will collect pregnancy information on any female subject who becomes pregnant while participating in this study. Pregnancy needs to be reported and followed-up as described in section 14.5 and section 14.5.5.

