## 6.3.5.2 Exclusion criteria

Subjects who meet **ANY** of the following criteria are **NOT** eligible for **repeat-treatment**:

- Occurrence of a related Serious Adverse Event or Adverse Event of Special Interest (i.e., embolic events with possible, probable, or causal relationship to an intravascular injection of the device, as changes in vision [loss of vision, blurriness, double vision, pain in or around the eye, blindness, blind spots, problems moving the eyes], skin changing color around the eyelids or around the site of injection, other embolic phenomenon, e.g., stroke, skin necrosis, or impending necrosis) during or after the baseline injection and/or touch-up injections
- 2. Occurrence of a related Adverse Event that occurred during the initial treatment phase, and is ongoing at the time of the repeat treatment (i.e., relationship is classified as "possible", "probable" or "causal relationship"; outcome is "not recovered / resolved", "recovering / resolving", "recovered / resolved with sequelae" or "unknown")
- 3. Subjects who experienced visual changes considered abnormal clinically significant or other serious medical conditions during or after the baseline or touch-up injections, respectively

- 4. Subjects who have one of the following assessments during the visual examinations: Snellen acuity test worse than 20/40 (with corrective eyewear, if applicable), abnormal confrontational visual field test, or abnormal ocular motility test
- 5. Subjects who became pregnant since start of the study or planning to become pregnant during the clinical investigation
- 6. Known human immune deficiency virus-positive individuals
- 7. Presence of infectious, inflammatory or proliferative cancerous or pre-cancerous lesions in the treatment area
- 8. Development of re-current (three times a year over the last year) herpes simplex in the treatment area since study start
- 9. Development of any autoimmune or connective tissue disease since study start, or current treatment with immuno-modulating therapy
- 10. Development of uncontrolled (or unstable) diabetes mellitus or systemic diseases since study start as per investigator discretion
- 11. Facial plastic surgery, tissue augmentation with silicone, fat or another non-absorbable substance (permanent fillers) and semi-permanent fillers (e.g., *poly-L-lactic* acid) in the area of device application and during the initial treatment phase of the investigation

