# 6.3.6 Withdrawal criteria and procedures

The subject **MUST** be withdrawn from the investigation for any of the following reasons:

1. Withdrawal of consent: At any time during the investigation and without giving reasons, a subject may decline to participate further. The subject will not suffer any disadvantage as a result.

The subject **MAY** be withdrawn from the investigation for any of the following reasons:

- 1. Occurrence of an AE which requires a premature termination of the treatment or precludes followup of the subject (e.g., COVID-19)
- 2. A major CIP deviation, which may interfere with evaluation of the treatment outcome (e.g., additional aesthetic correction of the defect during the course of the investigation, use of prohibited medication, or similar)
- 3. Investigator's decision, triggered by safety, behavioural or administrative reasons
- 4. Pregnancy; **Note:** pregnant women **must** be withdrawn from **further treatment**; However, pregnant women may remain in the study for safety assessments during the scheduled study visits.
- 5. Subjects with abnormal clinically significant changes in visual examination after treatment **must** be withdrawn from **further treatment** in case an eye specialist confirms that the result is related to a vascular injection of the dermal filler (see section 6.4.8 and section 16.1).

The subjects may remain in the study at least for safety assessments during the scheduled study visits.

6. Subjects who experience neurological symptoms indicative of a vaso-occlusional event after treatment **must** be withdrawn from **further treatment** in case a neurologist confirms that the result is related to a vascular injection of the dermal filler (see section 6.4.9, also see section 16.1).

The subjects may remain in the study at least for safety assessments during the scheduled study visits.

Reasons, circumstances and findings related to early withdrawal should be fully described in the subject's source records and the eCRF respecting the subject's rights.

Attempts should be made to perform an early termination visit, which should consist of the assessments planned for Visit 9 (SV1), Visit SV2 to SV4 or Visit RT5 (depending on the study phase) – also see section 6.5.16. In the event that the withdrawal is caused by an AE, the procedures stated in section 14 must be followed.

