## 14.3 AE/SAE documentation

For each AE the following must be reported:

- Description of the event (event term)
- Seriousness
- Start date
- Intensity
- Action taken with subject (none, medical and/or surgical / non-pharmaceutical procedure)
- Action taken with device (none [no action taken], device withdrawn [no touch-up treatment(s) / repeat-treatment due to AE], device interrupted [touch-up treatment(s) / repeat-treatment later than required by study design due to AE or injection interrupted due to AE during treatment session])
- Outcome
- End date (if applicable)
- The relationship to the device and procedure, respectively

The information will be documented in subject's source record and in the eCRF.

Each AE and any new information concerning these events has to be documented, even if the investigator feels that it is not connected with the device or procedure.

The AE will be described in precise, standard medical terminology. The investigator will attempt to establish a diagnosis of the event based on signs, symptoms, and/or other clinical information (including affected body site(s)). In such cases, the diagnosis will be documented as the AE and not the individual

signs/symptoms. In case of any injection site reaction the exact location (e.g., upper or lower lips) should be clearly noted.

Each AE should be reported separately. The investigator will record all AEs in subject's (medical) record and on the "Adverse Events" page of the eCRF. For SAEs, the "Serious Adverse Event Reporting Form" must also be completed. Complete description of all AEs should be also available in source documents of the subject.

Adverse events will be documented beginning after provision of informed consent until the last visit of the subject. The follow-up period will be prolonged outside the investigation, if a related AE is ongoing and not stabilized after 24 weeks after last injection of the repeat-treatment phase (see section 14.6 for details).

AEs initially observed during or after baseline treatment are defined as treatment-emergent AEs (TEAEs). AEs occurring after informed consent but before baseline treatment will be defined as non-TEAEs. Any medical condition that is present prior to day of screening should be considered as medical history (i.e., concomitant disease) and not recorded as an AE. If such condition, however, deteriorates after the device administration, at any time during the investigation, it should be reported as an AE.

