## 14.5 AE/SAE and pregnancy reporting requirements

#### 14.5.1 General AE/SAE reporting requirements

Note: For any AE (including a SAE) all appropriate sections of the eCRF must be completed.

Any SAE must be reported by the investigator to **the sponsor's representative immediately but not later than 24 hours** of awareness **of the event via Email**. Contact details will be provided in a separate manual.

This also applies to serious and non-serious AESIs (see section 14.1 for definition), any other embolic event (regardless of seriousness and / or relationship to device or procedure), and any significant AE, which in the investigator's opinion could affect the safety of the subjects taking part in the investigation or the conduct of the investigation.

In general, information about an SAE will be collected and recorded on the SAE Reporting Form. The SAE Reporting Form will be provided by the sponsor's representative to the investigational sites and will contain additional process information for how to report.

The investigator will be requested to supply as much detailed information as possible regarding the SAE that is available at the time of the initial contact. The investigator should also complete missing or requested information and submit follow-up reports until the SAE has resolved or, in the case of permanent impairment, until the SAE has stabilized.

The sponsor's representative will inform the sponsor about any SAEs immediately after becoming aware of the respective SAE report from the investigator.

Should an SAE occur after the final visit, which is considered at least possibly related to the device or procedure, such events should always be reported to CROMA-PHARMA GmbH or its representative, even after the end of the clinical investigation.

At the end of the clinical investigation, a reconciliation of all reported SAEs will take place and be enclosed as a list in the Clinical Investigation Report.

For further information on reporting and notification requirements per country for Investigators see sections below.

Detailed reporting by the sponsor or sponsor's representative to IRBs/ECs, all Investigators and regulatory authorities will follow pertinent national legislation described in detail in Safety Management Plan (SMP).

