#### 14.5.5 Pregnancy

Any pregnancy must be notified to the contact given above within the same timelines as an SAE (within 24 hours after being made aware of the pregnancy). The Pregnancy and Lactation Exposure Form will be provided by the sponsor's representative to the investigational sites and will contain additional process information for how to report. If pregnancy is associated with an SAE (e.g., if the mother is hospitalized for hemorrhage), a separate SAE Reporting Form must be filed in addition to Pregnancy and Lactation Exposure Form. The pregnant subject must be withdrawn immediately from further treatment, if applicable. The pregnant subject may remain in the study for safety assessments during the scheduled study visits.

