## 14.6 AE/SAE and pregnancy follow-up

The investigator will take all appropriate and necessary measures required for resolution of the AE.

All AEs must be followed-up by the investigator until recovery, or until the investigator determines that the subject's condition is stable, or subject's last day of the clinical investigation at the site, whichever occurs first. All subjects excluded from repeat-treatment should continue to be followed until the resolution of all ongoing, related AEs.

All SAEs/AESIs judged to be related to the device (SADEs) must be followed by the investigator until the subject has recovered, recovered with sequelae, died, or until the investigator determines that the subject's condition is stable, whichever occurs first.

In addition, those subjects who have a related AE ongoing (i.e., not recovered / not resolved) and not stabilized (i.e., recovering / resolving) after 24 weeks after last injection of the repeat-treatment phase will be followed for a longer follow-up outside the investigation. The follow-up for these subjects would continue until resolution (i.e., recovered / resolved) or stabilization of the condition (i.e., recovered / resolved) resolved with sequelae).

AEs to be followed outside the investigation will be reported to the sponsor's vigilance department using the Post-Study-AE-Follow-Up Form. Contact details and additional process information for how to report will be given on the respective form.

Any pregnancy must be followed-up until the pregnancy outcome at least once in each trimester and pregnancy outcome (including pregnancy duration and health status of a newborn or cause of premature termination, as applicable) will be reported to the sponsor's representative using a Pregnancy Query Form for the status of pregnancy. If it is still on-going at the end of the clinical investigation, follow-up will be continued outside of the context of clinical investigation.

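### Section 6.4.4 makes withdrawal from the study compulsory on pregnancy, whereas 6.3.6 and 14.5.5 require only that treatment stops and allow safety follow-up to continue

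*Protocol*

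**What the plan says.** Three sections of the current protocol body deal with a subject who becomes pregnant.

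- **Section 6.4.4 (Pregnancy test):** "Any female subject who becomes pregnant while participating in the investigation must be withdrawn from the study (also see section 6.3.6"). The paragraph that follows refers the reader to 14.5 and 14.5.5 for reporting and follow-up.
- **Section 6.3.6 (Withdrawal criteria and procedures):** the list of compulsory reasons for leaving the investigation has one entry, withdrawal of consent. Pregnancy is item 4 of the second list, headed "The subject MAY be withdrawn from the investigation for any of the following reasons". Its note makes withdrawal from further treatment compulsory, then adds that "pregnant women may remain in the study for safety assessments during the scheduled study visits".
- **Section 14.5.5 (Pregnancy):** further treatment stops at once, if applicable, and "The pregnant subject may remain in the study for safety assessments during the scheduled study visits".

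Three other provisions determine what is lost or kept when a subject leaves early. Section 14.3: "Adverse events will be documented beginning after provision of informed consent until the last visit of the subject". Section 14.6: "All subjects excluded from repeat-treatment should continue to be followed until the resolution of all ongoing, related AEs". Repeat-treatment exclusion 5 (6.3.5.2): "Subjects who became pregnant since start of the study or planning to become pregnant during the clinical investigation".

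**The concern.** Section 6.4.4 turns an option into an obligation and cites as its source the section that creates the option. The protocol has no precedence clause, and section 10 says that the sponsor grants no waivers. A site that keeps a pregnant subject for safety visits, as 6.3.6 and 14.5.5 allow, breaches a compulsory rule in 6.4.4. A site that follows 6.4.4 gives up follow-up that the other two sections were written to permit.

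What is at stake is scheduled safety observation. Adverse events are documented only up to the subject's last visit, so early withdrawal ends planned detection of new events and the routine visual examinations in a woman who has received the filler. Long-term safety is a stated objective (5.2.3). Pregnancy tests are scheduled at almost every on-site visit for women of childbearing potential, so sites will consult 6.4.4.

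**Working it through.** The protocol gives no figure to reproduce. The check compares the texts and then counts visits.

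**Step 1: the rules side by side**

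| Section | Leave the study? | Stop further treatment? | Stay for safety visits? |
|---|---|---|---|
| 6.4.4 | Compulsory | Implied | Not possible |
| 6.3.6, item 4 | Optional | Compulsory | Permitted |
| 14.5.5 | Not required | Compulsory, if applicable | Permitted |

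Withdrawing the subject satisfies all three sections. Keeping her satisfies two and breaches 6.4.4. The conflict is therefore that 6.4.4 removes the choice.

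**Step 2: which section is out of line**

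- 6.3.6 deliberately separates leaving the investigation from stopping further treatment. Items 5 and 6 (visual and neurological events) follow the same pattern as pregnancy.
- 6.5.17 lists suspected or confirmed pregnancy as a reason for an unscheduled visit and treats early termination as only a possible result.
- Repeat-treatment exclusion 5 covers women pregnant at any time since study start. Inclusion 2 (6.3.5.1) already requires completion of Visit 9 (SV1), so the exclusion would be largely redundant if every such woman had been withdrawn.

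Section 6.4.4 is the exception.

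**Step 3: size of the loss per affected subject**

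Inputs are the visits in Tables 1 and 3 that carry both adverse event collection and visual examination, in weeks after the last injection. They are Weeks 4, 8, 16, 24, 36 and 48 in the initial phase, and Weeks 4, 12 and 24 in the repeat phase. The condition is a positive urine test at a scheduled visit, the earliest post-treatment one being at Week 2.

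Maximum visits lost = number of scheduled visits after the positive test. Maximum weeks lost = last scheduled week minus week of the test.

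| Initial phase, positive at Week | Visits lost (max) | Weeks lost (max) |
|---|---|---|
| 2 | 6 | 48 − 2 = 46 |
| 4 | 5 | 48 − 4 = 44 |
| 8 | 4 | 48 − 8 = 40 |
| 16 | 3 | 48 − 16 = 32 |
| 24 | 2 | 48 − 24 = 24 |
| 36 | 1 | 48 − 36 = 12 |
| 48 | 0 | 0 |

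| Repeat phase, positive at Week | Visits lost (max) | Weeks lost (max) |
|---|---|---|
| 2 | 3 | 24 − 2 = 22 |
| 4 | 2 | 24 − 4 = 20 |
| 12 | 1 | 24 − 12 = 12 |
| 24 | 0 | 0 |

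The lower bound is 0 in every row, because 6.3.6 also lets the site withdraw her. Visits SV2 to SV4 add nothing: exclusion 5 bars her from repeat-treatment, so Visit 9 (SV1) would be her end of study visit (Table 1, footnote 24).

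**The case against.** The strongest reply is that the document largely corrects itself. The sentence in 6.4.4 points to 6.3.6, the dedicated withdrawal section, and the next paragraph points to 14.5.5. A site that follows either reference reaches the intended rule. This stands only in part: the references lead to a rule that contradicts the one just read, and nothing says which prevails.

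The second reply is that little is lost, and this mostly stands. 6.3.6 permits withdrawal on pregnancy, so only an option disappears. Several safeguards remain:

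- an early termination visit is to be attempted (6.3.6, 6.5.16), which may recover one assessment;
- pregnancy is notified within 24 hours (14.5.5) and followed at least once per trimester to outcome (14.6);
- device-related SAEs and AESIs are followed to recovery, sequelae, death or stability (14.6);
- late SAEs remain reportable (14.5.1: "Should an SAE occur after the final visit, which is considered at least possibly related to the device or procedure");
- subjects excluded from repeat-treatment are followed until ongoing related events resolve (14.6). That sentence does not clearly cover a pregnancy that arises after repeat-treatment.

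The third reply is that the visit counts are not absolute limits. This is correct. A pregnancy confirmed off-schedule before the Week 2 visit would add that visit: 6 + 1 = 7 in the initial phase and 3 + 1 = 4 in the repeat phase. The counts above hold for detection at a scheduled test.

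A subject withdrawn before Week 24 would also lack the primary rating and count as a non-responder in the FAS (7.3.7). That does not raise the severity. 6.3.6 and 14.5.5 keep her only for safety assessments, so correcting 6.4.4 would not guarantee a Week 24 score.

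**Conclusion.** The concern holds: section 6.4.4 is wrong as written, because it makes compulsory what 6.3.6 and 14.5.5 leave optional. Severity is minor. Given detection at a scheduled test, the loss attributable to 6.4.4 is 0 to 6 visits (0 to 46 weeks) in the initial phase and 0 to 3 visits (0 to 22 weeks) after repeat-treatment, per affected subject. The maximum assumes that she would otherwise have attended every remaining visit, and it gives no credit for an early termination visit. The effect across the trial cannot be sized, because the protocol states no expected number of pregnancies; required contraception suggests few. No effect on the primary endpoint is claimed.

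**What to change.** In 6.4.4, replace the requirement to leave the study with the rule of the other two sections, for example: *must be withdrawn from further treatment; she may stay in the study for the safety assessments at the scheduled visits (see sections 6.3.6 and 14.5.5)*. This is a one-sentence amendment. It adds no procedure, visit or data item and does not affect the sample size or the analysis.
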